### **21.2. Relationship to Study Device(s)**

The Investigator must assess the relationship of the AE/SAE to the study device as related or unrelated. See criteria in Table 21.2-1.

**Table 21.2-1: Criteria for Assessing Relationship of Study Device to Adverse Event**

Classification	Description
Unrelated	The adverse event is determined to be due to a concurrent illness or effect of another device/drug and is not related to the investigational product.
Related	
 
The adverse event is determined to be potentially related to the investigational product, and an alternative etiology is equally or less likely compared to the potential relationship to investigational product.
 
There is a strong relationship to investigational product, or recurs on re-challenge, and another etiology is unlikely.
 
There is no other reasonable medical explanation for the event.
 

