**Table 11.1-1: Study Event Schedule**

Assessment	Screening a	Baseline	Procedure	Within 1 Day Post-procedure	Prior to Discharge or 7 Days Post-Procedure	30 Days b (±7 Days) Office Visit	6 Months b (±30 Days) Office Visit	12 Months b (±30 Days) Office Visit	24–60 Months b [Annual] (±45 Days) Office Visit
CT angiogram of iliofemoral system m	X								
Annual imaging (rotational X-ray) n								X	X
QOL surveys o		X				X	X	X	X p
Procedural cine-angiography (including post-deployment aortogram) q			X						
Pacemaker interrogation r						X		X	
AE and ADE assessments s			X	X	X	X	X	X	
Device deficiencies, SAE, SADE, USADE, UADE and CEC event assessments t			X	X	X	X	X	X	X
4D CT imaging of prosthetic valve u						X		X	

- a: It is recommended that screening materials for CRC review be submitted electronically within 5 days of a scheduled CRC call in order to be considered for review (unless otherwise specified).
- b: All follow-up dates will be calculated from the date of the (attempted) index procedure (or randomization in randomized subjects where no implant is attempted). Visits must be an office/clinical visit, but may be done in-hospital should the subject be admitted at the time. Subjects who are enrolled but do not receive a study device (test or control) will be followed for 1 year to assess for safety but do not need to have protocol required TTE or ECG.
- c: Study-specific consent includes screening consent to perform required assessments that will be evaluated by the CRC to confirm subject eligibility. If the study Informed Consent Form is modified during the course of the study, study subjects will be re-consented as necessary.

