**Table 11.1-1: Study Event Schedule**

Assessment	Screening a	Baseline	Procedure	Within 1 Day Post-procedure	Prior to Discharge or 7 Days Post-Procedure	30 Days b (±7 Days) Office Visit	6 Months b (±30 Days) Office Visit	12 Months b (±30 Days) Office Visit	24–60 Months b [Annual] (±45 Days) Office Visit
------------	------------------------	----------	-----------	-----------------------------	---	---	---	--	--

Imaging Core Laboratory procedure guidelines (see study Manual of Operations). Results must be forwarded to the CT/X-Ray Core Laboratory for analysis. If additional imaging is performed (e.g., cardiac CT or MRI scan), data may be provided for analysis.

- o: Includes the Kansas City Cardiomyopathy and SF-12 QOL questionnaires. Baseline QOLs should be performed within 30 days prior to the index procedure.
- p: QOL survey at 36 and 60 months.
- q: Procedural cine-angiogram including final post-deployment aortogram of the ascending aorta must be done and sent to the CT/X-Ray Core Laboratory for analysis.
- r: For subjects who received a permanent pacemaker related to the index procedure, pacemaker dependence must be captured at the 30-day and 1-year visits via pacemaker interrogation. Pacemaker interrogation should also include assessment of the percentage of beats where the ventricles are paced.
- s: AEs and ADEs will be monitored and collected from the time of enrollment through 12-month follow-up. For subjects who do not receive the study device, AEs will be monitored through 1-year follow-up.
- t: Information on device deficiencies for the test and the control devices, as well as all SAEs, SADEs, UADEs, USADEs, and CEC events will be monitored and reported to Boston Scientific for all enrolled subjects from the time of enrollment through termination of the study. For subjects who do not receive a study device (test or control), the mentioned events will be monitored through 1 year post-index procedure. Please refer to Section 7.2 for a list of CEC events and Table 26.2-1 for definitions of these events, which specify data required for CEC adjudication. Complaint reporting of any device deficiencies for any commercially available products used should also be carried out using the manufacturer’s processes.

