**Table 21.1-1: Adverse Event Definitions**

Term	Definition a
Adverse Event (AE) Ref: ISO 14155:2011	Any untoward medical occurrence, unintended disease or injury or untoward clinical signs (including abnormal laboratory findings) in subjects, users or other persons, whether or not related to the investigational medical device  Note 1: This definition includes events related to the investigational medical device or the comparator. Note 2: This definition includes events related to the procedures involved. Note 3: For users or other persons, this definition is restricted to events related to investigational medical devices.
Adverse Device Effect (ADE) Ref: ISO 14155:2011	Adverse event related to the use of an investigational medical device Note 1: This definition includes adverse events resulting from insufficient or inadequate instructions for use, deployment, implantation, installation, or operation, or any malfunction of the investigational medical device. Note 2: This definition includes any event resulting from use error or from intentional misuse of the investigational medical device.
Serious Adverse Event (SAE) Ref: ISO 14155:2011	Adverse event that: 
 
• Led to a death
 
• Led to serious deterioration in the health of the subject, that either resulted in:                             
 
○ a life-threatening illness or injury, or
 
○ a permanent impairment of a body structure or a body function, or
 
○ in-patient or prolonged hospitalization, or
 
○ medical or surgical intervention to prevent life- threatening illness or injury or permanent impairment to a body structure or a body function,
 
 
 
• Led to fetal distress, fetal death or a congenital abnormality or birth defect
 
 Note: Planned hospitalization for a pre-existing condition, or a procedure required by the protocol, without serious deterioration in health, is not considered a serious adverse event.
Serious Adverse Device Effect (SADE) Ref: ISO 14155:2011	Adverse device effect that has resulted in any of the consequences characteristic of a serious adverse event.

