For the randomized cohort, event reporting (eCRF) is required beginning from the time of randomization.

For the roll-in, Lotus 21 mm Nested Registry, LOTUS Edge Nested Registry, roll-in with the 29 mm LOTUS Edge, LOTUS Edge 29 mm Nested Registry, and U.S. Continued Access Study cohorts, event reporting (eCRF) is required beginning from the time an attempt is made to insert the Lotus Valve System/LOTUS Edge Valve System into the subject's femoral artery.

Refer to Section 19 for the known risks associated with the study devices (test and control). Based on the VARC recommendations and definitions, the adverse events and/or safety endpoints requiring adjudication by the CEC include the following.

- Mortality: all-cause, cardiovascular, and non-cardiovascular
- Stroke: disabling and non-disabling
- Myocardial infarction (MI): periprocedural ( $\leq 72$  hours post index procedure) and spontaneous ( $> 72$  hours post index procedure)
- Bleeding events: life-threatening (or disabling) and major
- Acute kidney injury ( $\leq 7$  days post index procedure): based on the AKIN System Stage 3 (including renal replacement therapy) or Stage 2
- Vascular complications: major
- Repeat procedure for valve-related dysfunction (surgical or interventional therapy)
- Hospitalization for valve-related symptoms or worsening congestive heart failure (NYHA class III or IV)
- New permanent pacemaker implantation resulting from new or worsened conduction disturbances
- New onset of atrial fibrillation or atrial flutter
- Coronary obstruction: periprocedural ( $\leq 72$  hours post index procedure)
- Ventricular septal perforation: periprocedural ( $\leq 72$  hours post index procedure)
- Mitral apparatus damage: periprocedural ( $\leq 72$  hours post index procedure)
- Cardiac tamponade: periprocedural ( $\leq 72$  hours post index procedure)
- Prosthetic aortic valve malpositioning, including valve migration, valve embolization, or ectopic valve deployment
- TAV-in-TAV deployment
- Prosthetic aortic valve thrombosis
- Prosthetic aortic valve endocarditis

Details on the CEC events and procedures are outlined in the CEC charter. Tests and images required to adjudicate these events are specified in the event definitions (see Table 26.2-1).

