#### **21.4.2. Control Device Deficiencies**

Device deficiencies related to use of the control device (CoreValve) should be reported per the IFU and per applicable local/regional requirements. If an AE results from a device deficiency or other device issue, the AE must be reported on the appropriate eCRF.

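### The causality table is worded mainly for the investigational product and the control-deficiency instructions conflict, so device-relatedness and deficiency counts may not be comparable between arms

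*Combined protocol and SAP*

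**What the plan says.** **Causality.** Section 21.2 states: "The Investigator must assess the relationship of the AE/SAE to the study device as related or unrelated". It refers the investigator to Table 21.2-1 for the criteria. There, Unrelated covers an event due to concurrent illness or the "effect of another device/drug and is not related to the investigational product". The first Related bullet asks whether the event is "potentially related to the investigational product, and an alternative etiology is equally or less likely"; the second also names the investigational product; the third names no product. In Table 21.1-1 an ADE is an "Adverse event related to the use of an investigational medical device", and a SADE is an ADE with serious consequences.

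**Where ADE and SADE are assessed.** The CoreValve procedure list (Section 11.7.1) includes both. So do the 30-day, 6-month and 12-month visit lists (Sections 11.10.1 to 11.10.3), which are not restricted to the test arm.

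**Deficiencies.** Footnote t of Table 11.1-1 begins "Information on device deficiencies for the test and the control devices, as well as all SAEs" and requires this information to be reported to the sponsor for all enrolled subjects. It adds that manufacturer complaint reporting for commercial products should be carried out too. Section 11.7.1 lists a deficiency assessment for CoreValve procedures. Section 21.4.2, however, says: "Device deficiencies related to use of the control device (CoreValve) should be reported per the IFU and per applicable local/regional requirements". Section 21.3 says much the same.

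**The concern.** The object of the causality question changes between the instruction and the criteria. The instruction covers either device, while most of the criteria cover only the investigational one. For a control subject CoreValve is not the investigational product, so it can be read as the other device whose effects count as Unrelated. For a Lotus subject no such difficulty arises. Any resulting misclassification would therefore differ by arm, lowering recorded device-relatedness under CoreValve and leaving it unchanged under Lotus. A side-by-side table of device-related events or ADE/SADE counts would tend to look worse for Lotus than the truth.

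The deficiency instructions raise a different problem. A site working from Section 21.4.2 may file a CoreValve deficiency with the manufacturer and stop there. A site working from footnote t would also report it to the sponsor. With up to 60 centers, control deficiency counts could depend on which page each center followed.

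**Working it through.** No arithmetic reproduces or refutes a stated figure here. The check sets the relevant texts side by side.

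**1. What study device means.** Footnote b of Table 11.1-1 attaches test or control to the term, and Section 21.1 refers to the study devices as test and control. The heading of Section 21.2 and the title of Table 21.2-1 also use study device. The instruction therefore covers CoreValve.

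**2. What investigational product means.** Section 16 separates the investigational device (16.1, Lotus and LOTUS Edge) from the control device (16.2). Section 5.2 describes CoreValve as commercially available. In the protocol's own terms CoreValve is not investigational.

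**3. Applying the table to a CoreValve-caused event.**
- Unrelated: the cause is a device other than the investigational product, and the event is not related to that product. The wording is met.
- Related, first and second bullets: both require a link to the investigational product. They are not met.
- Related, third bullet: no other reasonable medical explanation. It names no product, so an investigator could use it.

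Unrelated is thus an available literal reading, but not the only one.

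**4. ADE and SADE.** Under Table 21.1-1 a CoreValve-caused event cannot be an ADE, because the definition requires an investigational device. Control-arm sites are nonetheless told to assess ADEs and SADEs through 12 months. The 24- to 60-month list (Section 11.10.4) omits ADE and is addressed to Lotus recipients, so the conflict is not present at every visit.

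**5. Deficiency reporting.**

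| Source | Lotus | CoreValve |
|---|---|---|
| Table 11.1-1, footnote t | Report to sponsor | Report to sponsor, with manufacturer reporting in addition |
| Section 11.7 procedure lists | Assess | Assess |
| Table 21.3-1, method | eCRF | eCRF (cell not split by device) |
| Table 21.3-1, timeline | Within 1 business day | Per IFU and local rules; no fixed timeline |
| Sections 21.3 and 21.4 | eCRF (21.4.1) | Per IFU (21.3, 21.4.2) and local requirements (21.4.2); no eCRF named for the deficiency itself |

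The first three rows agree for the two devices; the last two do not.

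**6. Reach.** The control arm has 304 of 912 randomized subjects, and 304 / 912 = one third. The wording matters only for those with an event attributed to CoreValve or a CoreValve deficiency, and the documents give no expected rate for either. If a share s of CoreValve-caused events is graded Unrelated through the literal reading, the recorded control count is (1 − s) times the true count. The documents do not fix s, which could lie anywhere from 0 to 1.

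**7. What does not depend on relatedness.** The primary safety composite (Section 7.1.1), the primary effectiveness composite (7.1.2) and the secondary endpoint (7.1.3) contain no causality criterion. Section 12.1.5 plans overall adverse event and SAE rates and names no device-related comparison.

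**The case against.** The strongest reply is that the intent is clear. The section heading, its text and the table title all say study device; the adverse event definition expressly includes the comparator; the deficiency definition covers any medical device; Section 17.2 has investigators assess relationship to the device or procedure for every event; and requiring ADE assessment in the CoreValve cohort shows that attribution to CoreValve was meant. The restriction in the ADE definition is cited to ISO 14155:2011, so it is an adopted standard definition. The eCRF is not among the documents and might ask the question correctly.

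Much of that stands, and it rules out several stronger inferences.

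- A reader might infer that the rules are written only for the investigational product. The definitions just listed show otherwise.
- A reader might infer that the control arm's device-related rate is 0% whatever the truth. The third Related bullet names no product, and sites may apply the table to the assigned device.
- A reader might infer that control deficiencies bypass the study database. Footnote t, Section 11.7.1 and the undivided method cell of Table 21.3-1 contradict this, and Section 21.4.2 itself requires an adverse event arising from a control deficiency to go on the eCRF.
- A reader might infer that control-device harm is hidden from the Data Monitoring Committee. Section 22.1.2 has it review all AEs and SAEs in the randomized cohort, and valve thrombosis, malpositioning, repeat procedure and similar events are adjudicated without relying on investigator attribution.

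The reply does not remove the conflict. Evident intent does not help an investigator who applies the criteria as printed, and Table 21.3-1 confirms that relationship to the device is recorded on the adverse event form.

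**Conclusion.** The point holds as an internal inconsistency with a possible differential effect between arms. The printed criteria allow a CoreValve-caused event to be graded Unrelated, and the ADE/SADE definitions exclude a device for which those categories must be assessed. The deficiency passages give control-arm sites instructions that do not agree and set no fixed control timeline. Relatedness, ADE/SADE and deficiency counts may therefore not be comparable between arms.

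The consequence is confined to those descriptive quantities. No endpoint, adjudicated event or overall AE/SAE rate changes, and no planned between-arm test uses relatedness. The size cannot be stated as a number of events: it depends on how many centers took the literal reading and on how the eCRF phrases the question, neither of which the documents show. It is worth correcting because the error, if it occurs, falls on one arm only and the correction is nearly free.

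**What to change.** - In Table 21.2-1, replace the investigational product with the study device received (test or control) throughout.
- In Section 21.1, state that device-related classification for study analysis, including ADE and SADE, applies to both devices. Leave regulatory UADE/USADE reporting unchanged.
- Reconcile Section 21.3, Table 21.3-1 and Section 21.4.2 with footnote t of Table 11.1-1 and Section 11.7.1, so that control deficiencies are also entered on the eCRF, in addition to the manufacturer's route.

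The cost is a few sentences in two tables and three short sections, plus an eCRF completion note. The control-arm assessments concerned are already scheduled, so no visit or test is added.

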**21.3. Investigator Reporting Requirements**

The communication requirements for reporting to BSC are as shown in Table 21.3-1.

*Note:* The “become aware date” for an event that requires reporting per the protocol is the date that study personnel listed on the Delegation of Authority Log identify or are notified of the event.

Centers should report control device-related deficiencies as per requirements in the control-device Instructions For Use.

**Table 21.3-1: Investigator Reporting Requirements**

Event Classification	Communication Method	Communication Timeline
Unanticipated Adverse Device Effect / Unanticipated Serious Adverse Device Effect (UADE/USADE)	Complete adverse event (AE) electronic case report form (eCRF) page with all available new and updated information	
 
Within 1 business day of first becoming aware of the event
 
Beginning from time of enrollment for all subjects
 
Terminating at the end of the study
 

	Provide copies of all relevant source documents requested by BSC	
 
As soon as possible after reporting the event
 

Serious Adverse Event (SAE) including Serious Adverse Device Effects (SADE)	Complete AE eCRF page with all available new and updated information	
 
Within 2 business days of first becoming aware of the event or as per local/regional regulations.
 
Beginning from time of enrollment for all subjects
 
Reporting required through the end of the study
 

	Provide all relevant source documentation (unidentified) for reported event	
 
When documentation is available
 

Adverse Event (AE)	Complete AE eCRF page	
 
As soon as possible before the next planned monitoring visit
 
Beginning from time of enrollment
 

**Table 21.3-1: Investigator Reporting Requirements**

Event Classification	Communication Method	Communication Timeline
		for all subjects • Reporting required through 12 months
Device Deficiencies, Failures, Malfunctions, and Product Nonconformities	Complete applicable eCRF fields/pages with all available new and updated information.	Investigational Device: • Within 1 business day of first becoming aware of the event and as per local/regional regulations • Beginning from time of Lotus Introducer sheath insertion for all subjects • Reporting required through the end of the study Control Device: • As required per IFU and as per local/regional regulations

**Note:** The AE eCRF page contains information such as date of AE, treatment of AE resolution, assessment of seriousness, and relationship to the device.

Abbreviations: AE=adverse event; BSC=Boston Scientific Corporation; eCRF=electronic case report form; IFU=Instructions for Use

**21.4. Device Deficiencies**

**21.4.1. Boston Scientific Device Deficiencies**

All Lotus Valve System/LOTUS Edge Valve System device deficiencies (including but not limited to failures, malfunctions, use errors, product nonconformities, and labeling errors) must be documented on the appropriate eCRF and, if possible, the device should be returned to BSC for analysis. Instructions for returning the investigational device will be provided in the study Manual of Operations. If it is not possible to return the device, the investigator should document why the device was not returned and the final disposition of the device. Device deficiencies should also be documented in the subject’s medical record.

Device deficiencies and other device issues should not be reported as AEs. Instead, they should be reported on the appropriate eCRF. If an AE results from a device deficiency or other device issue, the AE must be reported on the appropriate eCRF.

Device deficiencies that did not lead to an AE but could have led to a SAE if a) suitable action had not been taken, or b) intervention had not been made, or c) circumstances had been less fortunate must be reported as described in Table 21.3-1.

#### **21.4.2. Control Device Deficiencies**

Device deficiencies related to use of the control device (CoreValve) should be reported per the IFU and per applicable local/regional requirements. If an AE results from a device deficiency or other device issue, the AE must be reported on the appropriate eCRF.

#### **21.5. Reporting to Regulatory Authorities / IRBs / ECs / Investigators**

Boston Scientific Corporation will notify all participating study centers if UADEs, USADEs, SAEs, SADEs, or investigational device deficiencies occur which imply a possible increase in the anticipated risk of the procedure or use of the device or if the occurrence of certain SAEs/SADEs requires changes to the protocol or the conduct of the study in order to further minimize the unanticipated risks.

Boston Scientific Corporation is responsible for reporting AE information to all participating investigators and regulatory authorities as applicable according to local reporting requirements.

The PI is responsible for informing the IRB/EC, and regulatory authorities of UADEs, USADEs, SADEs, SAEs, Device Deficiencies and/or other CEC events as applicable according to local reporting requirements. A copy of the Investigator's reports and other relevant reports (if applicable) to the IRB/IEC must be provided to BSC in accordance with local requirements.

